7.4 Concomitant Medications, Treatments, and Procedures

All concomitant antibiotic use during study participation will be obtained via study questionnaires and recorded in the participant's study charts. No concomitant medications, treatment, and/or procedures are restricted while on study. Information about concomitant antibiotic use will be collected at each study visit via questionnaire. Concomitant antibiotic use information is collected to assess if the antibiotic is being used to treat a MRSA infection or could potentially impact colonization with MRSA.

7.5 Justification for Sensitive Procedures

A placebo is used to assess the true efficacy of retapamulin compared to no medication or spontaneous decolonization. The study is blinded to both the researchers and the participants to minimize any bias with study drug use.

7.5.1 Precautionary Medications, Treatments, and Procedures

There are no medication precautions, interactions or toxicities known with the study agent. Therefore, there are no instructions for medication or therapy avoidance or modification as part of this protocol.

7.6 Prohibited Medications, Treatments, and Procedures

There are no medications, treatments or procedures that are not permitted on study

7.7 Prophylactic Medications, Treatments, and Procedures

There will be no prophylactic medications, treatments or procedures provided as prophylaxis on study

7.8 Rescue Medications, Treatments, and Procedures

There will be no rescue medications, treatments or procedures provided as rescue on study

7.9 Participant Access to Study Agent at Study Closure

Participants who remain positive for MRSA colonization after their completion of study related procedures will be offered access to the study agent via open label through the NYU Investigational Pharmacy.. Once subjects have completed study visit #3 and the follow up cultures one month post decolonization are collected, if they remain positive the researchers will offer the study agent directly via the NYU Investigational Pharmacy. The participants that remain positive for colonization will be advised to use the ointment again twice a day for 5 days to the nares and peri-rectal area.

CONFIDENTIAL

This material is the property of the NYU School of Medicine and Langone Medical Center. Do not disclose or use except as authorized in writing by the study sponsor

Interventional Template Version: 28 APR 2017

After the final study closure has been completed, there will not be continued access to study agent. The study drug is commercially available through physician prescription.

8 Assessment of Safety

8.1 Specification of Safety Parameters

Safety parameters and adverse reactions/side effects will be recorded in the participants chart in the study database. No more than minimal adverse effects (local application site irritation) are anticipated from using the study agent. If adverse effects are encountered by participants and considered to be more than minimal affect it would be considered a study endpoint and adverse effects should subside with withdrawal of study agent. If more than minimal adverse effect is experienced (eg anaphylaxis or allergic reaction) it will be reported to the industry partner and the IRB.

If subject develops MRSA active clinical infection while on study protocol, they will be cared for per routine medical management for such infections. This is anticipated to be rare. This development of disease while on protocol will be reported to the IRB and industry sponsor. If available, the isolates from these cases of active disease will be collected and analyzed by study team members and [name] laboratory to assess the bacterium and resistance determinants. Bacterial strain isolates will be stored. No material containing subject DNA will be collected or stored.

8.1.1 Definition of Adverse Events (AE)

An **adverse event** (AE) is any symptom, sign, illness or experience that develops or worsens in severity during the course of the study. Intercurrent illnesses or injuries should be regarded as adverse events. Abnormal results of diagnostic procedures are considered to be adverse events if the abnormality:

- results in study withdrawal
- is associated with a serious adverse event
- is associated with clinical signs or symptoms
- leads to additional treatment or to further diagnostic tests
- is considered by the investigator to be of clinical significance

8.1.2 Definition of Serious Adverse Events (SAE)

Serious Adverse Event

Adverse events are classified as serious or non-serious. A **serious adverse event** is any AE that is:

- fatal
- life-threatening
- requires or prolongs hospital stay
- results in persistent or significant disability or incapacity
- an important medical event

Important medical events are those that may not be immediately life threatening, but are clearly of major clinical significance. They may jeopardize the subject, and may require intervention to prevent one of the other serious outcomes noted above..

All adverse events that do not meet any of the criteria for serious should be regarded as **non-serious adverse events**.

8.1.3 Definition of Unanticipated Problems (UP)

Unanticipated Problems Involving Risk to Subjects or Others

Any incident, experience, or outcome that meets all of the following criteria:

CONFIDENTIAL

This material is the property of the NYU School of Medicine and Langone Medical Center. Do not disclose or use except as authorized in writing by the study sponsor
Interventional Template Version: 28 APR 2017

- Unexpected in nature, severity, or frequency (i.e. not described in study-related documents such as the IRB-approved protocol or consent form, the investigators brochure, etc)
- Related or possibly related to participation in the research (i.e. possibly related means there is a reasonable possibility that the incident experience, or outcome may have been caused by the procedures involved in the research)
- Suggests that the research places subjects or others at greater risk of harm (including physical, psychological, economic, or social harm).

8.2 Classification of an Adverse Event

8.2.1 Severity of Event

For AEs not included in the protocol defined grading system, the following guidelines will be used to describe severity.

- **Mild** – Events require minimal or no treatment and do not interfere with the participant's daily activities.
- **Moderate** – Events result in a low level of inconvenience or concern with the therapeutic measures. Moderate events may cause some interference with functioning.
- **Severe** – Events interrupt a participant's usual daily activity and may require systemic drug therapy or other treatment. Severe events are usually potentially life-threatening or incapacitating.

8.2.2 Relationship to Study Agent

The clinician's assessment of an AE's relationship to study agent is part of the documentation process, but it is not a factor in determining what is or is not reported in the study. If there is any doubt as to whether a clinical observation is an AE, the event should be reported. All AEs must have their relationship to study agent assessed. In a clinical trial, the study product must always be suspect. To help assess, the following guidelines are used.

- **Related** – The AE is known to occur with the study agent, there is a reasonable possibility that the study agent caused the AE, or there is a temporal relationship between the study agent and event. Reasonable possibility means that there is evidence to suggest a causal relationship between the study agent and the AE.
- **Not Related** – There is not a reasonable possibility that the administration of the study agent caused the event, there is no temporal relationship between the study agent and event onset, or an alternate etiology has been established.

8.2.3 Expectedness

The PI and essential study team members will be responsible for determining whether an AE is expected or unexpected. An AE will be considered unexpected if the nature, severity, or frequency of the event is not consistent with the risk information previously described for the study agent.

8.3 Time Period and Frequency for Event Assessment and Follow-Up

The occurrence of an AE or SAE may come to the attention of study personnel during study visits and interviews of a study participant presenting for medical care, or upon review by a study monitor. All AEs including local and systemic reactions not meeting the criteria for SAEs will be captured on the appropriate RF. Information to be collected includes event description, time of onset, clinician's assessment of severity, relationship to study product (assessed only by those with the training and authority to make a diagnosis), and time of resolution/stabilization of the event. All AEs occurring while on

CONFIDENTIAL

This material is the property of the NYU School of Medicine and Langone Medical Center. Do not disclose or use except as authorized in writing by the study sponsor
Interventional Template Version: 28 APR 2017

study must be documented appropriately regardless of relationship. All AEs will be followed to adequate resolution.

Any medical condition that is present at the time that the participant is screened will be considered as baseline and not reported as an AE. However, if the study participant's condition deteriorates at any time during the study, it will be recorded as an AE. UPs will be recorded in the data collection system throughout the study.

Changes in the severity of an AE will be documented to allow an assessment of the duration of the event at each level of severity to be performed. AEs characterized as intermittent require documentation of onset and duration of each episode.

The PI will record all reportable events with start dates occurring any time after informed consent is obtained until 7 (for non-serious AEs) or 30 days (for SAEs) after the last day of study participation. At each study visit, the investigator will inquire about the occurrence of AE/SAEs since the last visit. Events will be followed for outcome information until resolution or stabilization.

All unresolved adverse events should be followed by the investigator until the events are resolved, the subject is lost to follow-up, or the adverse event is otherwise explained. At the last scheduled visit, the investigator should instruct each subject to report any subsequent event(s) that the subject, or the subject's personal physician, believes might reasonably be related to participation in this study. The investigator should notify the study sponsor of any death or adverse event occurring at any time after a subject has discontinued or terminated study participation that may reasonably be related to this study. The sponsor should also be notified if the investigator should become aware of the development of cancer or of a congenital anomaly in a subsequently conceived offspring of a subject that has participated in this study.

8.4 Reporting Procedures – Notifying the IRB

8.4.1 Adverse Event Reporting

Adverse Events will be reported by the PI/co-investigator to the IRB and industry partner (Aqua Pharmaceuticals). Serious adverse events will be reported within 7 days. Minor/minimal adverse events (local application site irritation) will be reported at the completion of the study.

8.4.2 Serious Adverse Event Reporting

Serious Adverse Events will be reported in written format by the PI/co-investigator to the IRB and the industry partner within 7 days. The PI will be responsible for completing and signing off on the SAE reports.

8.4.3 Unanticipated Problem Reporting

Incidents or events that meet the OHRP criteria for UPs require the creation and completion of an UP report form. It is the site investigator's responsibility to report UPs to their IRB and to the DCC/study sponsor. The UP report will include the following information:

- Protocol identifying information: protocol title and number, PI's name, and the IRB project number;
- A detailed description of the event, incident, experience, or outcome;
- An explanation of the basis for determining that the event, incident, experience, or outcome represents an UP;
- A description of any changes to the protocol or other corrective actions that have been taken or are proposed in response to the UP.

To satisfy the requirement for prompt reporting, UPs will be reported using the following timeline:

CONFIDENTIAL

This material is the property of the NYU School of Medicine and Langone Medical Center. Do not disclose or use except as authorized in writing by the study sponsor
Interventional Template Version: 28 APR 2017

- UPs that are SAEs will be reported to the IRB and to the DCC/study sponsor within 7 days of the investigator becoming aware of the event.
- Any other UP will be reported to the IRB and to the DCC/study sponsor within 30 days of the investigator becoming aware of the problem.
- All UPs should be reported to appropriate institutional officials (as required by an institution's written reporting procedures), the supporting agency head (or designee), and OHRP within 30 days of the IR's receipt of the report of the problem from the investigator.

8.4.4 Reporting of Pregnancy

If pregnancy were to occur while participants are on study protocol, they will be withdrawn from the study and study drug use will be discontinued. The pregnancy will be reported in written format to the IRB and the industry partner by the PI.

8.5 Reporting Procedures – Notifying the Study Sponsor

The study clinician will complete a SAE Form within the following timelines:

- All deaths and immediately life-threatening events, whether related or unrelated, will be recorded on the SAE Form and submitted to the DCC/study sponsor within 24 hours of site awareness. See Section 1, Key Roles for contact information.
- Other SAEs regardless of relationship will be submitted to the DCC/study sponsor within 72 hours of site awareness.

All SAEs will be followed until satisfactory resolution or until the site investigator deems the event to be chronic or the adherence to be stable. Other supporting documentation of the event may be requested by the DCC/study sponsor and should be provided as soon as possible.

As a follow-up to the initial report, within the following 48 hours of awareness of the event, the investigator shall provide further information, as applicable, on the unanticipated event or the unanticipated problem in the form of a written narrative. This should include a copy of the completed Unanticipated Problem form, and any other diagnostic information that will assist the understanding of the event. Significant new information on ongoing unanticipated adverse effects shall be provided promptly to the study sponsor.

8.6 Study Halting Rules

Administration of study agent will be halted when three grade 3 AEs determined to be "probably related" are reported to the DCC. In the case of this study agent, retapamulin, that would likely be serious allergic reaction or anaphylaxis. The DCC will notify the study sponsor and investigators immediately when the third grade 3 event is reported and enrollment screens will stop accepting new study participants. The study sponsor will inform the DSMB members within 24 hours of this occurrence and will provide the DSMB with AE listing reports. The DSMB will convene an ad hoc meeting by teleconference or in writing as soon as possible. The DSMB will provide recommendations for proceeding with the study to the study sponsor/NIH. The study sponsor will inform the FDA of the temporary halt and the disposition of the study.

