8.7 Safety Oversight

It is the responsibility of the Principal Investigator to oversee the safety of the study. This safety monitoring will include careful assessment and appropriate reporting of adverse events as noted above, as well as the construction and implementation of a site data and safety-monitoring plan. Medical monitoring will include a regular assessment of the number and type of serious adverse events. The safety oversight will be conducted via a single medical monitor. It is felt that this is sufficient for this trial as the overall risk to the subjects is very low based on the number of subjects to be recruited, the type of non-invasive monitoring to be performed, and the safety profile of the drug to be studied.

CONFIDENTIAL

This material is the property of the NYU School of Medicine and Langone Medical Center. Do not disclose or use except as authorized in writing by the study sponsor

Interventional Template Version: 28 APR 2017

Safety oversight will be under the direction of a medical monitor with appropriate expertise, [name], MPH. [name] is a Pediatric Infectious Diseases physician and Microbiologist at NYU with expertise in both of these fields. The medical monitor will meet with the PI and co-investigator at least semiannually to assess safety and efficacy data on each arm of the study. Data collected to date will be reviewed including participants' demographics, any significant history or illnesses, % change in colonization for nose and peri-rectal area, and answers to questionnaires. Safety data will also be reviewed including any adverse effects that have occurred, side effects reports and retention/dropout rate. The medical monitor will provide its input to the PI, IRB and industry partner.

9 Clinical Monitoring

Clinical site monitoring is conducted to ensure that the rights and well-being of human subjects are protected, that the reported trial data are accurate, complete, and verifiable, and that the conduct of the trial is in compliance with the currently approved protocol/amendment(s), with GCP, and with applicable regulatory requirement(s).

- Monitoring for this study will be performed by [name], MPH.

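### The halting rule in section 8.6 cannot be applied as written: it counts AE categories that section 8.2 does not record, and it gives the post-halt recommendation to a DSMB although section 8.7 provides a single medical monitor

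*Combined protocol and SAP*

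**What the plan says.** Section 8.6 sets a numeric trigger: "Administration of study agent will be halted when three grade 3 AEs determined to be" probably related, once reported to the DCC. It adds that for retapamulin this would most likely mean a serious allergic reaction or anaphylaxis. At the third event the DCC notifies the sponsor and investigators, and "enrollment screens will stop accepting new study participants". The DSMB is then informed within 24 hours and convened. "The DSMB will provide recommendations for proceeding with the study to the study sponsor/NIH."

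Section 8.2.1 introduces its severity scale with the words "For AEs not included in the protocol defined grading system, the following guidelines will be used to describe severity" and lists Mild, Moderate and Severe. Of the top level it says: "Severe events are usually potentially life-threatening or incapacitating." Section 8.2.2 has two levels. Related applies where "The AE is known to occur with the study agent, there is a reasonable possibility that the study agent caused the AE", or where there is only a link in time. Everything else is Not Related.

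Section 8.7 states: "The safety oversight will be conducted via a single medical monitor." It calls this sufficient given the low risk, has the monitor meet the PI and co-investigator at least semiannually, and gives the reporting line: "The medical monitor will provide its input to the PI, IRB and industry partner."

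Section 10.4.7.1 adds a separate ground: enrollment and dosing stop if SAEs are seen in multiple participants, with no count and no relatedness condition. Section 10.4.7.2, headed Efficacy Review, repeats it.

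**The concern.** A stopping rule is useful because it can be applied mechanically to the trial's own records when there is little time to debate it. Here the safety database will hold no AE labelled grade 3 and none labelled probably related unless a scale outside the supplied text is used. Someone would have to decide, after the events have happened, which records count. The question of whether to proceed would then be addressed to a DSMB, while the section that sets up oversight says a single medical monitor does that work. The monitor has no stated part in the 8.6 process, and no section in the supplied text sets a deadline for an individual event to reach that person.

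What is at stake is a prompt and consistent safety decision in a pediatric trial. The drug is applied to the nares and peri-rectal area, and section 2.4.1 says it has not been widely evaluated on mucosal surfaces.

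**Working it through.** The protocol gives no derivation for the count of three, so there is no figure to reproduce. The check is a comparison of sections.

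| Element | Section 8.6 | Elsewhere in the protocol |
|---|---|---|
| Severity | grade 3 | Mild / Moderate / Severe (8.2.1); no numeric grades |
| Causality | probably related | Related / Not Related (8.2.2) |
| Who reviews | DSMB | one medical monitor (8.7) |
| Who is advised | sponsor/NIH | PI, IRB, industry partner (8.7) |
| Funder | NIH implied | company grant and a donation; NIH not named (15.1) |

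**Severity.** Severe is the natural counterpart of grade 3, but no section says so. The lead-in to 8.2.1 allows for another grading system, which is not in the supplied text.

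**Causality.** This gap remains even if such a grading system exists, because 8.2.2 refers to no other relatedness scale. A two-level scale cannot separate probably from possibly related, and Related also covers a temporal link alone. Take three Severe events, one clearly attributable to the drug and two linked only in time, and assume a link in time is not enough for probably related. The 8.6 count is then 1 of 3 on the narrower label and 3 of 3 on Related. The choice of mapping can decide whether the trial halts.

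**Route to the reviewer.** Deaths and immediately life-threatening events reach the DCC/sponsor in 24 hours and other SAEs in 72 hours (8.5). Unanticipated problems that are not SAEs have 30 days (8.4.3). More-than-minimal adverse effects go to the industry partner and IRB with no deadline (8.1). Serious events that may be adverse reactions go to the study team and IRB within one day (10.4.4). None of these routes names the medical monitor. Semiannual meetings over the 2-year study guarantee only 2 / 0.5 = 4 scheduled contacts.

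**Relation to 10.4.7.1.** Three cases, reading 8.6 as Severe and Related:
- Two children with related anaphylaxis: 8.6 stands at 2 of 3 and does not halt. 10.4.7.1 halts if multiple means two.
- Three Severe, Related, non-serious AEs: 8.6 halts and 10.4.7.1 does not.
- Two unrelated readmissions: 8.6 stands at 0 of 3. Read literally, 10.4.7.1 halts.

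The first case matters for the fix. If 10.4.7.1 were folded into the three-event rule, no pre-specified rule would stop dosing after two related anaphylaxis cases.

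**The case against.** The strongest reply is that 8.6 looks like template wording whose intent is clear. It says the trigger would in practice be serious allergic reaction or anaphylaxis, and such events would plausibly be rated Severe and Related. The halt itself follows from the count and needs no DSMB. A child with a serious reaction leaves the study or stops the drug individually (2.4.1, 10.4.5), the PI is responsible for safety (8.7) and assesses serious events (10.4.4), and 5.8 allows suspension for unacceptable risk. All of this stands and is why severity is low. It does not supply the missing mapping or say who advises on proceeding.

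Three stronger readings are tempting, and the documents do not support them.
- A reader might infer that 8.6 and 10.4.7.1 conflict and that one must govern. Each states a sufficient condition and neither says only if, so both can stand. 10.4.7.1 also speaks of a halt being deemed necessary, which permits judgment.
- A reader might infer that 10.4.7.1 would stop the trial on routine admissions. Section 8.3 treats conditions present at screening as baseline unless they worsen, and the documents give no SAE rate from which to estimate how often the trigger would be met.
- A reader might infer that no DSMB, DCC or grading system exists. Parts of the roles and administration pages are not in the supplied text, and 8.7 refers to a site data and safety-monitoring plan that is not included. The point rests on the explicit single-monitor wording in 8.7, not on the absence of a listing.

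**Conclusion.** The point holds as an inconsistency in a stated safety rule. Followed literally, 8.6 counts events in categories that 8.2 does not record and sends the recommendation on proceeding to a body that 8.7 does not use.

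Its size is small. Expected harm is low: a 5-day topical course, application-site irritation in under 2% of patients in clinical studies (2.4.1), and an earlier nasal trial with no reported side effects (2.2.2). The safeguard is weakened rather than absent, and no endpoint, data item or efficacy analysis is affected. It is still worth correcting, because the rule would have to be interpreted at the moment it is needed.

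The conclusion assumes that no grading scale, relatedness scale or monitoring plan outside the supplied text resolves the labels. If one does, a cross-reference would settle the trigger. The mismatch between 8.6 and 8.7 on who reviews would remain unless that plan addresses it.

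**What to change.** - **8.6, trigger.** Restate it as three AEs that are Severe (8.2.1) and Related (8.2.2), with the threshold confirmed by the sponsor and IRB. Related is broader than probably related, so the count may be reached slightly sooner. That is a small cost and errs toward caution.
- **8.6, reporting.** Require each such event, serious or not, to reach the medical monitor within the 72-hour limit that 8.5 already uses for SAEs, or 24 hours if life-threatening.
- **8.6, review.** Replace the DSMB and NIH with the medical monitor advising the PI, IRB and sponsor, convened when the trigger is met and not held for the semiannual meeting.
- **10.4.7.1.** Keep it as an additional ground for halting, limited to SAEs judged Related in two or more participants and reviewed by the same monitor. This preserves a halt after two related anaphylaxis cases. Clusters of unrelated SAEs would then be handled under 5.8.
- **10.4.7.2.** Delete the misplaced copy of the safety wording.
- **10.6.3.** Do not tie unblinding of all participants to the halt count. Otherwise three events, whatever their arm, could unblind the 54-child trial before any review.

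The cost is one protocol amendment and some added reporting to the existing monitor. No new committee, visit or data item is needed.
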